6.3 Methods of Minimising Bias

6.3.1 Randomisation

The active and maintenance treatment phase consists of a 1:1 randomized placebo-controlled allocation sequence for the 36-week study period. A dynamic computerized 1:1 randomisation stratified for age, gender, type of treatment (in- or outpatient) and hsCRP across each site will be applied. A minimisation algorithm integrated in SecuTrial® will provide a balanced distribution between the two treatment groups (active/ placebo) for each site and strata.

Access to the SecuTrial® generated randomisation list will be restricted to the Clinical Trial pharmacist, in case of an interim analysis to the IDMC, upon request to the regulatory authorities

and to the data management at the USZ CTC. The study medication will be labelled at the KAZ and will be sent out to the study sites in two batches.

The algorithm and allocation process is implemented in SecuTrial and the development of the algorithm is done by the data manager of the Clinical Trial Centre and cannot be influenced by the investigators. The clinicians and researchers who enrol the patients just provide the relevant stratification data. The minimization algorithm contains an element of chance so that even with the knowledge of all previous allocations the next allocation cannot be determined.

Participants, parents, treating clinicians and doctors, research assistants, all involved researchers including the PI remain blind to the allocation of participants to the study drug (active/ placebo). SecuTrial® only provides one single randomisation number making it impossible to guess the allocation. Data analyst (PD Dr. rer. nat. [name], [name]) will only get access to the randomisation code list after completion of data entry, double entry of a subset of data and final closure of the database. The only person who has access to the computer-generated allocation code is the data manager of the CTC and the clinical trial pharmacist of the Clinical Trials Pharmacy of the Universities of Zürich (*Kantonsapotheke Zürich KAZ*).

If deemed necessary, the IDMC is allowed to review unblinded data as further specified in the IDMC SOP.

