Omega-3 Fatty Acids as First-Line Treatment in Pediatric Depression

Statistical Analysis Plan for [name], [name]

[name] ([contact])

[name]

Version 1.0 of May 23, 2022

List of abbreviations

AD	antidepressant
AE	adverse event
CDRS-R	Children's Depression Rating Scale - Revised
DIKJ	Children's Depression Inventory (Depressionsinventar für Kinder und Jugendliche)
EPA	eicosapentaenoic acid
KIDscreen-CAT-27	quality of life questionnaire
pMDD	pediatric major depressive disorder
SIQ-Jr	Suicide Ideation Questionnaire-Junior
SUSAR	Suspected Unexpected Serious Adverse Reaction

Introduction

1 Type of trial

This is a 36-week multi-center 1:1 randomized, double-blind, placebo-controlled, two-armed, parallel group study investigating the superiority of EPA-rich Omega-3 to placebo in the treatment of children and adolescents with pediatric major depressive disorder. The randomization included a minimization algorithm based on the following factors: site, age (8-12 vs. 13-18), gender (male vs. female), and hsCRP (<1 mg/l; 1-3 mg/l; >3mg/l). For sites offering both in- and out-patient care, in-/out-patient type was used as an additional minimization factor. The trial aimed to recruit children/teenagers between 8 and 18 years old with a primary diagnosis of major depressive disorder (DSM-IV, K-SADS-PL) and at least moderate depressive symptoms (CDRS-R ≥ 40).

In order to include a representative sample of moderately and severely ill children with major depressive disorders, the use of clinically required SSRIs is permitted. The anticipated proportion of patients receiving additional antidepressants at some point during follow-up is estimated to be around 30%. The use of additional antidepressants is expected to influence primary outcome measurements and be influenced by treatment group, with greater antidepressant use hypothesized in the control arm. Antidepressant use may therefore bias the estimation of the omega-3 treatment effect.

2 Scope of the statistical analysis plan

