Missing data By design, several baseline model covariates cannot be missing, as they are required for minimization during randomization. We distinguish between study dropouts and intervention dropouts. Study dropouts are participants whom withdraw consent, are monotone not available for follow-up visits, or are removed from the trial according to the protocol due to non-compliance (< 60% pills taken). Intervention dropouts are participants whom newly initiate an off-trial antidepressant or are newly prescribed an increased dose of an off-trial antidepressant prescribed before baseline.

Methods to handle missing data are outlined per analysis type below. Where multiple is used, 50 imputed datasets will be computed. Results across datasets will be combined using Rubin's rule.

Modeling In case of covariate imbalance on baseline covariates other than antidepressant use, omega-3 index, age, gender, and hsCRP, these covariates will also be included in the models described below. In case of computational convergence issues, simpler models will be estimated.

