where time t is considered a factor (while also investigating possibility of linearizing time effect) and randomized treatment group (intervention) and the interaction between randomized treatment group and time are included as fixed effects. The baseline values of the minimization factors age, gender, and hsCRP, as well as baseline antidepressant use and omega-3 index are included as covariates. The baseline outcome measure is modeled in the response, not as a covariate. The terms b_{i0} , b_{i1} , and b_{s0} represent participant-specific random intercepts and slopes and site-specific random intercepts. The random effects are assumed to be normally distributed and an unstructured covariance matrix will be assumed. The error term $\varepsilon_i(t)$ is assumed to be normally distributed with mean zero and variance σ^2 , independent of the random effects and is independent over time. An overall treatment effect for CDRS-R score at 36 weeks ($\beta_1 + \beta_{11}$) will be reported with a 95% confidence interval and corresponding p -value.

The competing survival models for time to event r (intervention dropout or study dropout) take the form:

$$\lambda_{ir}(t) = \lambda_{0r} \exp\{\gamma_1 \text{intervention} + \alpha_r m_i(t)\}$$

where the cause-specific Cox models include intervention as a time-independent effect and the estimated true trajectory of CDRS-R as a time-varying effect. The parameters α_r measure the strength of association between the longitudinal outcome and risk of the corresponding dropout event.

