7.2 Secondary endpoints

7.2.1 Confirmatory secondary endpoints

The binary confirmatory secondary outcomes include:

- **Remission**, defined as a CDRS-R total score < 28 at any time up until 36 weeks
- **Response**, defined as a 30% drop in CDRS-R total score at any time up until **12 weeks**
- **Intervention dropout**, defined as initiation of non-randomized antidepressant use while on trial for participants not on a non-randomized antidepressant at baseline or an increase in antidepressant dose while on trial for participants on a non-randomized antidepressant at baseline

Unadjusted proportions per treatment arm will be presented with 95% confidence intervals. To adjust for baseline antidepressant use, omega-3 index, and CDRS score, as well as the minimization factors age, gender, and hsCRP, these binary outcomes will each be assessed using log-binomial models with treatment arm as the effect of interest. Each model will be interpreted in terms of the adjusted risk ratio (RR) comparing the outcome probability in the omega-3 group to that in the placebo group ($RR_{\text{omega-3/placebo}}$). The null hypothesis that the risk ratio is equal to 1 (no difference in risk across treatment groups) will be rejected if the 95% confidence interval for the risk ratio does not include 1. If the 95% confidence interval for the risk ratio is above 1, omega-3 treatment will be considered superior.

These models will include data from all randomized participants and analyze the participant data according to the treatment arms participants were randomized to (as-randomized). Data after intervention dropout will be considered missing. Multiple imputation under MAR will be used to impute longitudinal CDRS-R scores for study and intervention dropouts before the binary outcomes are determined. MI will be performed separately within each treatment arm (White et al 2011) using imputation models containing the minimization factors, baseline antidepressant use and omega-3 index.

As for the primary outcome, a delta-based sensitivity analysis approach will be used to address MNAR. For analysis of intervention dropout, imputation is only needed for participants with study dropout before intervention dropout and no sensitivity analysis is planned.

The continuous confirmatory secondary outcomes include:

- self-reported **quality of life** measured by the KIDscreen-CAT-27 overall score at 36 weeks
- **Depression severity** measured by DIKJ at 36 weeks

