These continuous outcomes will each be assessed using ANCOVA linear regression models with the 36-week measurement as the outcome, treatment arm as the effect of interest, and the baseline measurement, antidepressant use, omega-3 index, CDRS-R score, and the minimization factors age, gender, and hsCRP as covariates.

The treatment coefficient denotes the mean difference in outcome score across the treatment groups. The null hypothesis that the mean scores are equal across treatment groups will be rejected

if the 95% confidence interval for the treatment group coefficient does not include 0. If the 95% confidence interval for the treatment group coefficient is above 0 for KIDscreen-CAT-27 (below 0 for DIKJ), omega-3 treatment will be considered superior with respect to its effect on quality of life (depressive symptoms).

These models will include data from all randomized participants and analyze the participant data according to the treatment arms participants were randomized to (as-randomized). Data after intervention dropout will be considered missing. Multiple imputation under MAR will be used to impute scores at 36 weeks for study and intervention dropouts. MI will be performed separately within each treatment arm (White et al 2011) using imputation models containing the minimization factors, baseline antidepressant use, omega-3 index, and baseline score. As for the primary outcome, a delta-based sensitivity analysis approach will be used to address MNAR.

Sub-domains will be described with tables or figures.

The final confirmatory secondary outcome is:

- the time on trial before initiation of new or increased antidepressant use (intervention dropout).

A Kaplan Meier approach will be used to estimate unadjusted median time to this event overall and per treatment arm. A log rank test will be used to compare time to intervention dropout across treatment arms.

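### Care setting was a minimisation factor but is in no analysis model, and site is missing from the confirmatory secondary analyses: a free improvement, minor in size

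*SAP*

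**What the plan says.** **Allocation.** SAP section 1: "The randomization included a minimization algorithm based on the following factors: site, age (8-12 vs. 13-18), gender (male vs. female), and hsCRP". It continues: "For sites offering both in- and out-patient care, in-/out-patient type was used as an additional minimization factor". Protocol 6.3.1 agrees, describing a randomisation "stratified for age, gender, type of treatment (in- or outpatient) and hsCRP across each site will be applied". SAP section 8 records that unit type was added as a factor after funding and peer review.

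**Primary analysis (SAP 7.1).** "The baseline values of the minimization factors age, gender, and hsCRP, as well as baseline antidepressant use and omega-3 index are included as covariates". Setting is not listed. Site does appear: the random terms "represent participant-specific random intercepts and slopes and site-specific random intercepts". The Cox sub-models contain treatment arm and the modelled CDRS-R trajectory, with no direct term for setting or site. The SIQ-Jr model (7.2.2) is built by analogy.

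**Confirmatory secondary analyses (SAP 7.2.1).** The binary-outcome models adjust for three baseline measurements: CDRS score, omega-3 index and antidepressant use. On the allocation factors the SAP says: "as well as the minimization factors age, gender, and hsCRP, these binary outcomes will each be assessed using log-binomial models". The ANCOVAs for KIDscreen and DIKJ use the same three minimisation factors. For time to antidepressant start: "A log rank test will be used to compare time to intervention dropout across treatment arms". No strata are named.

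**Conditional rule (SAP section 7, Modeling).** "In case of covariate imbalance on baseline covariates other than antidepressant use, omega-3 index, age, gender, and hsCRP, these covariates will also be included". No criterion for imbalance is given. The imputation models refer to the minimisation factors without listing them.

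**The concern.** When allocation is balanced on a factor that predicts outcome and the analysis then ignores it, the tests are conservative. Continuous-outcome intervals are wider than they need to be, and time-to-event comparisons lose power.

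The protocol makes a link plausible. Section 8.7.1 presents admission and starting an antidepressant as responses to the same lack of improvement. Section 8.7.2 leaves the antidepressant decision to the treating team, independently of the researchers, so practice could differ by site and setting. Antidepressant start is a confirmatory endpoint and also the event on which the joint model is built.

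The conditional rule does not close the gap. It admits a covariate only when it is imbalanced, which minimisation is meant to prevent. A balanced prognostic factor is exactly the case that costs efficiency.

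**Working it through.** **1. The plan's own figures.** The documents give no power or interval width for the antidepressant-start comparison. The responder calculation in SAP 6.2 reproduces: [1.96·√(2·0.5·0.5) + 0.8416·√(0.24+0.24)]² / 0.20² = 96.9, so 97 per arm; 97/0.9 = 107.8, so 108 per arm and 216 in total. In SAP 6.1, 74 per arm (SMD 0.54, 90% power) reproduces. For SMD 0.4 at 80% power the t-test needs 100 per arm; the stated 111 is matched only after 10% loss (99.1/0.9 = 110.1). That does not affect this point.

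**2. Which factor is in which analysis.**

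| Analysis | Age, gender, hsCRP | Setting | Site |
|---|---|---|---|
| CDRS-R mixed model | yes | no | random intercept |
| Cox sub-models | only via CDRS-R | no | only via CDRS-R |
| Log-binomial models | yes | no | no |
| ANCOVAs | yes | no | no |
| Log-rank test | no | no | no |

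Site reaches the Cox sub-models because the site intercept b_s0 is part of m_i(t), which enters the hazard multiplied by α_r. This carries a site's CDRS-R level. It cannot represent sites that prescribe differently at equal severity.

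**3. Continuous outcomes.** Let R² be the share of residual variance that the omitted balanced factor explains beyond terms already in the model. The documents do not give it, so 2, 5 and 10% are assumptions.

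- Interval inflation = 1/√(1−R²) − 1
- Actual two-sided type I error = 2·[1 − Φ(1.96/√(1−R²))]
- Power after adjustment, from a nominal 80% = Φ(2.80/√(1−R²) − 1.96)

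| R² | Interval too wide by | Type I error | Nominal 80% becomes |
|---|---|---|---|
| 2% | 1.0% | 4.8% | 81% |
| 5% | 2.6% | 4.4% | 82% |
| 10% | 5.4% | 3.9% | 84% |

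Balanced allocation already lifts the unadjusted analysis slightly above its nominal power. At 100 per arm (80.4% nominal), ignoring versus adjusting gives 80.6 v 81.2%, 81.0 v 82.3% and 81.6 v 84.3%. The net gain is 0.6, 1.3 and 2.7 points.

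**4. Log-rank test of antidepressant start.** From the SAP: about 30% start an antidepressant. Assumed: the treatment and setting hazard ratios (HR) and the setting mix. Both simulations use n = 220.

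- Simulation A: treatment HR 0.55; minimisation on the SAP factors with an assumed biased coin of 0.8; site sizes from Protocol section 7; two mixed, two inpatient-only and three outpatient-only sites assumed; 15% loss rate; about 62 events; 2,000 runs; error about 1 point for power and 0.5 for type I error.
- Simulation B: treatment HR 0.5; 40% inpatients; about 31% events; 4,000 runs; error about 0.7 points for power.

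Power, unstratified v stratified by setting:

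| Setting HR | A | Loss | B | Loss |
|---|---|---|---|---|
| 1 | 63.8 v 63.8% | 0 | 67 v 67% | 0 |
| 2 | 62.0 v 63.4% | 1.4 | 67 v 69% | 2 |
| 3 (A), 2.8 (B) | 61.4 v 66.2% | 4.8 | 66 v 68% | 2 |
| 5 (A), 4.9 (B) | 53.4 v 62.6% | 9.2 | 64 v 70% | 6 |

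Type I error of the unstratified test in A is 4.8, 4.4, 3.6 and 3.3% down the rows. In B it is 4.6-4.9% for setting HRs of 1.6 to 2.8 and about 3% at 4.9.

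The mechanism here is dilution of the hazard ratio towards the null. In B at a setting HR of 4.9 the model standard error of the log hazard ratio was 0.28 with and without stratification. Adding setting to a Cox model would therefore not narrow its interval.

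**5. Risk ratio for antidepressant start.** In A, the standard error of the crude log risk ratio exceeded the setting-stratified one by 0 to 9% across setting HRs of 1 to 5. The SAP's log-binomial model already adjusts for other baseline variables, so its gain may be smaller.

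**6. Site as well.** Adding one fixed set of site effects to A (log-hazard SD 0.4, assumed) and stratifying by site and setting gave losses from 0.3 points (62.5 v 62.8%) to 13.8 (47.4 v 61.2%). This is one illustration at assumed values.

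**The case against.** The strongest reply is that nothing in the documents says how strongly setting or site predicts outcome. Protocol 8.7 standardises background treatment on the S3 guideline. The loss could be nil, and up to a setting HR of 2 it is within about 2 points. That stands, and the size must be given as a range starting at zero.

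Second, part of the effect is already captured. At single-setting sites, site determines setting, so the CDRS-R site intercept absorbs some of it. Baseline antidepressant use and CDRS score in the log-binomial models may carry some of the severity behind setting. The imputation models may also include site and setting. This lowers the likely gain, but it leaves setting differences within mixed sites, and it does not help the log-rank test, which has no covariates.

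Third, more terms may cause non-convergence in log-binomial models or in Cox sub-models with about 65 events (30% of 220 is 66), and the SAP's fallback to simpler models is undefined. That is fair and calls for a stated order of simplification.

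A reader might infer three stronger things that the documents do not support:

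- *That site is ignored in every analysis of antidepressant start.* It is not: b_s0 sits inside m_i(t).
- *That intervals are certainly too wide and the comparison certainly loses about 7 points of power.* One such result, 62 v 69% with type I error 3.3 v 5.6%, assumes 55% of inpatients and 15% of outpatients start an antidepressant. That implies a setting HR of −ln(0.45)/−ln(0.85) = 0.799/0.163 = 4.9, the strong end of the range.
- *That the omission could produce a false finding of benefit.* The direction is conservative.

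**Conclusion.** The omission is in the text: setting is in no specified analysis model, and site is in no confirmatory secondary analysis, although the trial allocated on both. The consequence is conditional. If these factors predict outcome or prescribing beyond the terms already present, the plan gives up some efficiency: 1 to 5% of interval width for continuous outcomes at R² of 2 to 10%, and 0 to about 9 points of log-rank power for setting HRs of 1 to 5. Type I error falls to about 3% only at the strong end. All of these rest on assumed prognostic strength, and the antidepressant figures also on an assumed treatment HR of 0.5 to 0.55. If setting is not prognostic, stratifying by it costs nothing measurable (63.8 v 63.8%). This is a free improvement of minor severity.

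**What to change.** Before unblinding, amend the SAP to:

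- add in-/outpatient status at randomisation as a fixed covariate to the CDRS-R and SIQ-Jr mixed models, the Cox sub-model for antidepressant start, the log-binomial models and the ANCOVAs;
- add site to the secondary models where they converge, pooling small sites by a rule fixed in advance;
- stratify the log-rank test by setting;
- list by name the minimisation factors used in the imputation models;
- state that site is the first term dropped if a log-binomial model does not converge.

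No new data are needed: Protocol 7.3 has site and treatment type entered in the randomisation form. The cost is one or a few degrees of freedom and a small convergence risk, which the stated order of simplification handles. It also removes the discretion in the present rule on imbalanced covariates, as far as these two factors are concerned.

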9.3.2 Visit 1: baseline visit

The baseline visit takes place at the end of the placebo-lead-in phase. First, depressive symptoms will be assessed with the CDRS-R and the subscale depressive disorders of the K-SADS-PL. Parent's ratings can be obtained in person or over the phone. If the patient still fulfils the diagnosis of a major depressive disorder with at least moderate severity, the patient is enrolled using the computerized 1:1 randomization procedure described above. Current medication use, AEs and the Medication Adherence Reporting Scale is assessed. Clinician rate the patient according to the CGI, CGAS, and the HoNOSCA. Depressive symptoms will be further assessed with the Children's Depression Inventory (DIKJ), the Beck Hopelessness Scale II (BHS), the Beck Anxiety Inventory (BAI II), the suicidal ideation questionnaire and the Insomnia Severity Index. Further self-reported questionnaires are filled in by the patients including the Perceived Stress Scale (PSS-10), the Connor-Davidson Resilience Scale, the KIDscreen-Cat-27, the Strength and Difficulty Questionnaire (SDQ), and the IES-27-J. In patients > 13 years of age, self-rating questionnaires shall be completed with help of the parents or the research investigators. Patients > 13 years shall complete the questionnaires themselves (parents are instructed not to influence the patient's self-ratings). Self-rating questionnaires may be directly entered online into the data base by the patients / families themselves. Perceived side effects will be assessed with the Antidepressant Side Effect Checklist (ASEC). At the end of the baseline visit, study medication will be dispensed for the first time and new appointments will be scheduled.

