7.1.2 Sensitivity analyses for the primary endpoint

1. **Typical ITT analysis:** In order to compare results with other trials, the linear mixed model part of the analysis model above will be applied to the full analysis set, with all participants analyzed as randomized. The data from intervention dropout participants will be used as observed, i.e, the outcomes observed while on non-randomized antidepressants will be used. The mixed model assumes that missing data is missing at random. This analysis is expected to be biased toward the placebo arm, as the number of participants requiring antidepressants is expected to be higher in the placebo arm and the additional antidepressant will improve outcomes.
2. **Modified ITT analysis:** The first sensitivity analysis will be repeated, but the data from intervention dropout participants will be considered missing in the mixed model upon non-randomized antidepressant initiation/dose increase. The responses of participants with missing data will be assumed similar to those with complete data and similar covariate characteristics. The bias resulting from imbalance in the use of non-randomized antidepressants across treatment groups is curtailed, but the amount of data available for analysis, and therefore power, is diminished.
3. **Typical PP analysis:** In order to address the efficacy estimand, the sensitivity analysis model above will be applied to all full analysis set data during which participants were 'on protocol'. This means the participants are adhering to the treatment they were randomized to and are not using additional antidepressants. Non-compliers and those taking non-randomized antidepressants are excluded completely (i.e., complete case analysis). This yields an estimate of efficacy that is unbiased under the MAR assumption. It assumes that participants with missing data (those with additional antidepressants and those not adhering to randomized treatment) would have had similar outcomes to participants completing the study in the same treatment arm and with similar baseline characteristics and score trajectories. However, the use of additional anti-depressants is not considered to be random across participants, but rather related to intermediate outcomes and possibly treatment assignment. Selection bias is then expected to affect this estimate. Additionally, the reduction in participants decreases the power to detect a treatment effect.

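### The primary model lets the arms differ freely at baseline and reports the week-36 level, so it gains little or no precision from baseline CDRS-R

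*SAP*

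**What the plan says.** SAP 7.1 fits a linear mixed model to CDRS-R at baseline and weeks 6, 12, 24 and 36, linked to two Cox models for dropout. Time is a factor, although a linear form is to be explored. The fixed effects include a treatment main effect (β1) and a treatment term at every visit, baseline included (β7 to β11). On baseline the SAP says: "The baseline outcome measure is modeled in the response, not as a covariate". The reported result is "An overall treatment effect for CDRS-R score at 36 weeks", which is β1+β11.

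Protocol 9.3.2 gives the order of events at the baseline visit. "First, depressive symptoms will be assessed with the CDRS-R and the subscale depressive disorders of the K-SADS-PL"; if the patient still qualifies, "the patient is enrolled using the computerized 1:1 randomization procedure described above".

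The confirmatory secondary analyses (SAP 7.2.1) treat baseline differently. The log-binomial models are specified "To adjust for baseline antidepressant use, omega-3 index, and CDRS score, as well as the minimization factors age, gender, and hsCRP". The ANCOVA models use the outcome's own baseline together with "antidepressant use, omega-3 index, CDRS-R score, and the minimization factors age, gender, and hsCRP as covariates".

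In SAP 7.1.2, sensitivity analysis 1 says "the linear mixed model part of the analysis model above will be applied to the full analysis set", and analysis 2 repeats it with data after antidepressant start set to missing. Analysis 3 uses the same model, but "Non-compliers and those taking non-randomized antidepressants are excluded completely".

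**The concern.** Putting baseline in the response vector adjusts for it only if the arms are forced to share one baseline mean. Here the baseline arm difference, β1+β7, is a free parameter, so it absorbs whatever imbalance occurred and passes no correction to week 36. The reported quantity is a level difference, not a change from baseline, so baseline is not subtracted either.

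Baseline severity is not a minimisation factor (SAP 1), so the design does not balance it directly. In any one trial, a chance imbalance carries into the primary estimate in proportion to the baseline-to-week-36 correlation, and the interval is wider than the collected data allow. The outcome measured at baseline is already in the database, and the secondary models use it.

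**Working it through.** **The plan's own figure.** SAP 6.1 gives 111 per arm for SMD 0.4, 80% power and two-sided 0.05. The noncentral t calculation gives 99.08 per arm, and 99.08/0.90 = 110.1, rounded up to 111. So 111 reproduces once 10% loss is included. This is a plain t-test that takes no credit for baseline, so the stated power does not depend on the point made here.

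**Complete data, time as a factor.** Let d0 and d36 be the arm differences in means at baseline and week 36, with SD 1 at both visits and correlation ρ.

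- Free baseline (SAP): estimate = d36, variance 2/n. The ratio to a model with no baseline visit was 1.000 at every ρ examined.
- Common baseline: estimate = d36 − ρ·d0, variance (2/n)(1 − ρ²).

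In a simulation at ρ = 0.43, the free estimate correlated 0.43 with the baseline imbalance and the constrained estimate 0.00.

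**Inputs with censoring.**

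- Randomised: 225 + 20 = 245, plus up to 20 more = 265 (Protocol 6.2), so 122.5 to 132.5 per arm, all in the full analysis set (SAP 7).
- Uncensored at week 6: 1 − (21 + 20)/225 = 0.818, from 21 early dropouts (Protocol 6.2) and about 20 early antidepressant starts (Protocol 6.3.2).
- Uncensored at week 36: 0.70 × (1 − 21/225) = 0.635, from the anticipated 30% antidepressant use (SAP 1).
- Weeks 12 and 24 by interpolation: 0.781 and 0.708.
- Covariance (assumed): random intercept and slope, baseline and week-36 variance 1, residual variance 0.3. With time scaled 0 to 1, the intercept variance is 0.7, the intercept-slope covariance ρ − 0.7 and the slope variance 1.4 − 2ρ.
- ρ is not in the documents; 0.10 to 0.60 is assumed.

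The variance of the week-36 contrast comes from generalised least squares, inverting the sum of X′V⁻¹X over dropout patterns, with 10 free means against 9 when baseline is shared. Power = Φ(0.4/SE − 1.96).

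| ρ | Variance ratio, common/free | Interval narrower | Power at 122.5 per arm, free to common | Power at 132.5 per arm, free to common |
|---|---|---|---|---|
| 0.10 | 0.993 | 0.3% | 72.7 to 73.0% | 76.0 to 76.3% |
| 0.25 | 0.957 | 2% | 73.6 to 75.4% | 76.9 to 78.6% |
| 0.40 | 0.887 | 6% | 75.0 to 79.9% | 78.2 to 82.9% |
| 0.50 | 0.817 | 10% | 76.3 to 84.2% | 79.5 to 86.9% |
| 0.60 | 0.726 | 15% | 78.0 to 89.3% | 81.1 to 91.5% |

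Example at ρ = 0.40 and 122.5 per arm: the free SE is 0.1518. The common SE is 0.1518 × √0.887 = 0.1430, and Φ(0.4/0.1430 − 1.96) = Φ(0.837) = 79.9%. The ratios do not depend on n, and residual variance 0.2 or 0.4 moves the cuts by at most 0.3 points.

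**What the free model already recovers.** Under this censoring, baseline rows help fill in missing later values and cut the variance by 0.6% to 6% across the five correlations, against a model without the baseline visit. A separate calculation with 40% spread-out dropout gave 0.3% to 3.8% for ρ from 0.15 to 0.60.

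**Sensitivity analysis 1.** With only the 21/225 = 9.3% early loss missing, the cuts are 0.9%, 5.7%, 14.7%, 23.2% and 33.8%.

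**Chance imbalance, complete data.** One standard error is √(2/n) = 0.128 SD (n = 122.5) or 0.123 SD (n = 132.5). Multiplied by ρ of 0.10 to 0.60, it shifts the week-36 estimate by 0.012 to 0.077 SD, which is 3% to 19% of SMD 0.4.

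**Reasons the gain may be smaller.**

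- The entry rule of CDRS-R 40 or more truncates baseline. If it removes the lowest 10% to 30% of a normal distribution, ρ = 0.40 becomes 0.35 to 0.29 (cut roughly 9% to 6%) and 0.60 becomes 0.53 to 0.46 (21% to 16%).
- If existing covariates explain 10% of variance at both visits in the same direction, ρ becomes (ρ − 0.10)/0.90, and the cuts at 0.25, 0.40 and 0.60 are 2%, 8% and 23%.

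**The case against.** The strongest reply is that nothing here is an error. A model with separate baseline means is valid, and the gain rests on a correlation the documents do not supply.

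**Size.** Applying the truncation and covariate discounts together leaves cuts of about 0.5% to 1% at a nominal 0.25, 3% to 5% at 0.40 and 11% to 17% at 0.60. Censoring may also be heavier than assumed, because later loss, withdrawal and non-adherence are not counted; with 50% uncensored at week 36, the cuts are 0.5%, 3.5%, 9.5%, 15.5% and 23.6%. This stands as a limit on size. It moves the answer within the range shown and does not reverse it.

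**Linear time.** If time is linearised, baseline rows do inform the fitted line and already cut the week-36 variance by 4% to 9%. That is correct. Sharing the baseline mean would still cut a further 0.0%, 2.8%, 10.3%, 18.4% and 29.3%. The factor form is the stated model.

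**Imbalance rule.** The modelling paragraph of SAP 7 adds other imbalanced baseline covariates. It gives no threshold, depends on the data, and sits beside an explicit statement that baseline CDRS-R is not a covariate. It does not settle the matter.

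**Process.** Protocol 11.4.2 includes a treatment main effect, and Protocol 2.10 lists changes to the form of statistical analysis among those the ethics committee authorises. Both need acknowledging when the change is documented.

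**Conclusion.** The point holds and is worth acting on, as an improvement rather than the repair of an error. As written, the primary contrast gets nothing from baseline CDRS-R with complete data and only a little with censoring, although a common baseline mean is justified by the order of scoring and randomisation.

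The size is uncertain. Before discounts, the variance cut runs from 0.7% to 27% over assumed correlations of 0.10 to 0.60. The entry threshold and the expected recovery of about 60% within 9 months (Protocol 3.1.1) may put the true value towards the lower end, where the gain is a few percent or less. Precision was not worse in any scenario computed.

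These figures cover the linear submodel with known covariance and assumed dropout. The full joint model with its two Cox parts was not simulated, but nothing in those parts constrains the baseline arm difference.

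**What to change.** **Primary model and sensitivity analyses 1 and 2.** Give both arms one baseline mean: remove the treatment main effect and the baseline-by-treatment term, keep treatment terms for weeks 6, 12, 24 and 36, and report the week-36 term. If time is linearised, remove the treatment main effect. The same edit should settle the coding, since an intercept plus all five visit indicators, and a main effect plus all five interactions, are redundant as written.

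**Sensitivity analysis 3.** Use baseline CDRS-R as a covariate instead. Exclusions there follow randomisation, so equal baseline means are not guaranteed. This does not remove the selection bias that the SAP already acknowledges.

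**Carry-over.** State whether the SIQ-Jr model (SAP 7.2.2), built by analogy, and the omega-3 index interaction test (SAP 7.1.1) follow the revised form.

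**Minor.** In-/outpatient type is absent from the outcome models, and site from the log-binomial and ANCOVA models, although both were minimisation factors. Add them where the models converge; the expected gain is small.

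**Cost.** SAP wording and a refit; no patients, visits or new data. The SAP is dated May 23, 2022, after the database closure scheduled for the end of April 2022 in the protocol synopsis. Record the change, and check whether it needs ethics committee authorisation under Protocol 2.10, before the analysts receive the randomisation list (Protocol 6.3.1). If that point has passed, report the constrained model as supplementary.
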